9.17.2. Tumor Assessment for Brain Tumors

Patients will be evaluated for response by Gd-MRI. All Gd-MRIs (standard brain tumor MRI including both precontrast and postcontrast images using a Gadolinium (Gd) chelate as the contrast agent) should be performed when the patient is on a stable dose of steroids for at least 7 days. Gd-MRI will be performed at the following time points:

- Screening within 28 days prior to Day 1 of Cycle 1. Gd-MRI scans obtained prior to the signed ICF may be used as the screening scan if they were obtained within 28 days of the first dose of TAS-120.
- At the end of every 2 cycles (up to +2 weeks), up to Cycle 4, until documented progression (including after end of treatment if the patient discontinues for reasons other than radiologic disease progression).
- Following Cycle 4, at least after every 3 cycles (\pm 7 days) or as clinically indicated.
- At end of treatment (EOT), a Gd-MRI scan must be performed if the prior scan was performed \geq 9 weeks prior to discontinuation of TAS-120 treatment if the patient discontinued for reasons other than radiologic disease progression.

If a patient has a response, response confirmation should be obtained through tumor assessments/scans 4 to 6 weeks after the first documentation of response. Patients must then return to their original schedule of assessments.

Neurological examination for patients with brain tumors must always be performed within one week of the date of the Gd-MRI as part of the response assessment. Response will be based on RANO criteria.

All patients' files and radiological assessments must be available for source verification and may be submitted for extramural review for final assessment of antitumor activity. Results of any unscheduled evaluations should be recorded in the patient's source documents.

9.18. Patient-Reported Outcomes

Two Patient-Reported Outcome (PRO) instruments, EuroQol-5D measure of health-related quality of life (EQ-5D) and the European Organization for Research and Treatment of Cancer Quality of Life Questionnaire (EORTC QLQ-C30) will be used in the Phase 2 part of the study. EQ-5D is a standardized measure of health status as patient-reported outcome assessment. EORTC QLQ-C30 is an integrated system for assessing the health-related quality of life of cancer patients participating in international clinical trials. These assessments will be collected at the following time points (as close as possible to the time points when tumor assessment is performed):

- Screening within 28 days prior to Day 1 of Cycle 1.
- At the end of every 2 cycles (up to +2 weeks), up to Cycle 4.
- Following Cycle 4, at least after every 3 cycles (\pm 7 days) or as clinically indicated.
- At end of treatment (EOT)

9.19. End-of-treatment Visit

An end-of-treatment (EOT) visit is required for all living patients who discontinue treatment. The EOT visit must be performed 0-7 days after the decision is made to discontinue study treatment (for patients who discontinue at a planned study visit, that visit may be considered the EOT visit if all assessments required at EOT are performed).

9.20. 30-Day Safety Follow-up

A safety follow-up visit will be conducted 30 days after the last dose of TAS-120. If the patient starts new anticancer therapy within 30 days of the last dose of TAS-120, the 30-day safety follow-up visit should be performed prior to the start of new anticancer therapy within the 30-day window. If the evaluation of EOT and 30-day Safety Follow-up is within ± 14 days, only the 30-day Safety Follow-up will be performed. If the patient is unable to return to the site prior to the initiation of new treatment, a follow-up phone call can be conducted by the site to collect any new safety information that occurred between discontinuation of study treatment and the initiation of the new anticancer treatment.

9.21. Survival Status Follow-up

Overall survival status will be collected during the survival follow-up period every 3 months (± 2 weeks) from the patient's previous visit.

For the Phase 1 Expansion part of the study, patients should be followed for up to 12 months after the last patient enrolled in this phase of the study.

For Phase 2, patients should be followed for up to 18 months after the last patient enrolled in this part of the study.

CCI

10. EFFICACY ASSESSMENT CRITERIA

10.1. Efficacy Assessment for Solid Tumors

The determination of antitumor efficacy will be based on objective tumor assessments made by the investigator according to the revised RECIST guidelines (version 1.1, 2009) of unidimensional evaluation.¹⁷

For Phase 1 Expansion, the primary endpoint is ORR (and EPR for GBM or grade III glioma) and the secondary endpoints of DOR, DCR, PFS, and OS.

For Phase 2, the primary endpoint is ORR and the secondary endpoints of DOR, DCR, PFS, PROs and OS.

Primary endpoints will be based on the independent review of images by the Core Imaging Laboratory. In addition, for the Phase 2 part of the study, sensitivity analyses for some key efficacy endpoints (eg, ORR, and PFS) will be performed based on investigators or local radiologist assessments.

The RECIST guideline (version 1.1, 2009) instructs those conducting oncology trials designed with a primary endpoint that is response-related to require confirmation of response after a minimum of 4 weeks.

10.1.1. Method of Imaging

All patients with and without measurable disease will be eligible for assessment. The same method of assessment and the same technique should be used to characterize each identified and reported lesion at Screening and during follow-up. Imaging-based evaluation is preferred to evaluation by clinical examination when both methods have been used to assess the antitumor effect of treatment. All measurements should be recorded in metric notation using a ruler or calipers.

Contrast enhanced CT scans or MRIs are the preferred methods for tumor assessments. If a contrast agent is contraindicated in a patient, obtain a non-contrast chest CT and enhanced MRI of the abdomen (and pelvis if clinically indicated). A spiral CT should be performed using a 5 mm or less contiguous reconstruction algorithm. Images must be acquired of the chest and abdomen (and pelvis if clinically indicated or obtained at Baseline) at each time point. Only CT scans and MRI may be used for tumor measurement.

Clinical lesions will only be considered measurable when they are superficial (e.g., skin nodules, palpable lymph nodes). In the case of skin lesions, documentation by color photography, including a ruler to estimate the size of the lesion, is recommended.

Ultrasound should not be used to measure tumor lesions that are clinically not easily accessible for overall response evaluation (e.g., visceral lesions). Ultrasound is a possible alternative to clinical measurements of superficial palpable nodes, subcutaneous lesions, and thyroid nodules. Ultrasound might also be useful to confirm the complete disappearance of superficial lesions usually assessed by clinical examination.

For additional guidance refer to the revised RECIST guidelines (version 1.1, 2009)¹⁷ specifications for standard anatomical radiological imaging, which are included in the Imaging Manual.

10.1.2. Tumor Definitions

Measurable Lesions:

- Measurable visceral lesions: Lesions that can be accurately measured in at least 1 dimension with the longest diameter (to be recorded) ≥ 10 mm by CT scan if using slice thickness of 5 mm or less, or at least double the slice thickness of the CT or MRI scan if the slice thickness is > 5 mm.
- Measurable pathological lymph nodes: A malignant lymph node must be considered pathologically enlarged with high suspicion of metastasis and measure ≥ 15 mm in the short axis when assessed by CT scan. The short axis is defined as the longest linear dimension perpendicular to the node's longest diameter as assessed within the same plane that the scan was acquired.

Only measurable lesions can be selected as target lesions.

Non-measurable lesions include:

- Small visceral metastatic lesions that have a longest dimension less than 10 mm, or if slice thickness is greater than 5 mm, less than twice the slice thickness.
- Abnormal and suspected metastatic lymph nodes that are ≥ 10 mm to < 15 mm in the short axis.
- Truly non-measurable lesions (e.g., ascites and peritoneal carcinomatosis).

All non-measurable lesions can only be selected as non-target lesions.

Target Lesions:

- All measurable lesions up to a maximum of 2 lesions/organ and 5 lesions in total, representative of all involved organs/tissues should be identified as target lesions.
- Target lesions should be selected on the basis of their size (visceral lesion with the longest diameter and lymph node with the measurement of short axis), be representative of all involved organs/tissues, but in addition should be those that lend themselves to reproducible repeated measurements.
- When recording tumor measurements, the longest diameter will be measured for each non-nodal target lesion. For measurable pathological lymph nodes that may be identified as target lesions, the short axis measurement will be combined with the measurements of non-nodal (i.e., visceral lesion) target lesions. Therefore, in cases of complete response (CR) when abnormal nodes have been used as target lesions, the sum of diameters will not reduce to a null value.
- Target lesions will be followed up and measured at each subsequent time point.
- The sum of the diameters for all target lesions will be calculated and recorded. The baseline sum will be used as a reference to further characterize any objective tumor assessment in the measurable dimension of the disease.

- Assign a measurement to all target lesions regardless of size. An option of “too small to measure” will be provided if a measurement cannot be assigned. A value of zero should only be assigned in the case of a CR.
- An option of “not assessable” for a lesion will only apply to lesions that cannot be read due to technical reasons, for example:
 1. CT artifact.
 2. Patient positioning where the lesions are obstructed or cannot be seen.
 3. Lesions that may not be seen in their entirety due to CT slice thickness.
- In cases where a lesion divides into 2 lesions, the longest diameters of the fragmented portions should be added together to calculate the target lesion sum.
- In cases where 2 lesions coalesce, a plane between them may be maintained that would aid in obtaining maximal diameter measurements of each individual lesion. If the lesions have truly coalesced such that they are no longer separable, the vector of the longest diameter in this instance should be the maximal longest diameter for the “coalesced lesion.”

Non-target Lesions:

Non-target lesions include all non-measurable lesions and measurable lesions that have not been selected as target lesions.

The primary lesion should always be classified as a non-target lesion irrespective of its size and whether or not it can be accurately measured.

Lymph nodes that have a short axis < 10 mm are considered non-pathological and should not be recorded.

Any equivocal lesion without clear diagnosis (e.g., uncharacteristic solitary lung nodule without biopsy, uncharacteristic thyroid mass lesion without fine needle aspiration) may be considered a non-target lesion if it cannot be differentiated from a benign lesion.

All other lesions (or sites of disease), including pathological lymph nodes, should be identified as non-target lesions and should also be recorded at Baseline. Measurements are not required, but their presence, absence, or unequivocal progression should be followed throughout the study.

It is possible to record multiple non-target lesions involving the same organ as a single item on the eCRF (e.g., multiple enlarged pelvic lymph nodes or multiple liver metastases).

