 - h. **Group 8 (Enrollment Suspended as of Amendment 7):** Patient has any tumor type not included in one of the prior groups, harboring FGFR gene fusions or activating mutations.
- b. Phase 2
- i. Patient has histologically or cytologically confirmed, locally advanced, metastatic, unresectable iCCA harboring FGFR2 gene fusions or other FGFR2 rearrangements based on results from *either* of the following (see Section 9.1 for details):
 - a. Testing by Foundation Medicine:
 - i. As part of study pre-screening; or
 - ii. Previously tested by Foundation Medicine; in this case, it is requested that tumor tissue be provided to Foundation Medicine if available.
 - b. Local laboratory testing using next generation sequencing [NGS], fluorescence in situ hybridization [FISH], or other assays that can determine FGFR2 gene fusions or other FGFR2 rearrangements on tumor tissues or from ctDNA. It is requested that patients enrolled on this basis provide tumor tissues to Foundation Medicine, if available from either archival samples or fresh tumor biopsy.
 - ii. Patient has been treated with at least one prior systemic gemcitabine and platinum-based chemotherapy. Patients with prior adjuvant gemcitabine-platinum chemotherapy are eligible if the patient had recurrence within 6 months of the last dose of the regimen.

- iii. Patient has documentation of radiographic disease progression on the most recent prior therapy
4. Patient has measurable disease as defined by Response Evaluation Criteria in Solid Tumors (RECIST) guidelines (version 1.1, 2009) for advanced solid tumors or RANO criteria (2010) for brain tumors.
5. Eastern Cooperative Oncology Group (ECOG) performance status 0 or 1 on Day 1 of Cycle 1 (see [Appendix C](#), ECOG Performance Status).
6. Able to take medications orally (e.g., no feeding tube).
7. Adequate organ function as defined by the following criteria:
 - a. Aspartate aminotransferase (AST) and alanine aminotransferase (ALT) $\leq 3.0 \times$ upper limit of normal (ULN); if liver function abnormalities are due to underlying liver metastasis, AST and ALT $\leq 5 \times$ ULN.
 - b. Total bilirubin $\leq 1.5 \times$ ULN, or ≤ 3.0 mg/dL for patients with Gilbert's syndrome.
 - c. International normalized ratio (INR) < 1.3 (or < 3.0 on anticoagulants)
 - d. Absolute neutrophil count $\geq 1000/\text{mm}^3$ (i.e., $\geq 1.0 \times 10^9/\text{L}$ by International Units [IU])

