10.1.3.1. Target and Non-Target Response Assessments

Assessments will be based on the definitions below.

TARGET LESIONS	
Lesions Response:	Definition:
Complete Response (CR)	The disappearance of all target lesions. Any pathological lymph nodes must have reduction in short axis to < 10 mm.
Partial Response (PR)	At least a 30% decrease in the sum of diameters of the target lesions, taking as a reference the baseline sum diameters.
Progressive Disease (PD)	At least a 20% increase in the sum of diameters of the target lesions, taking as a reference the smallest sum on study, including the baseline sum. In addition to the relative increase of 20%, the sum must also demonstrate an absolute increase of at least 5 mm. Definitive new lesion presence also indicates progression.
Stable Disease (SD)	Neither sufficient shrinkage to qualify for PR nor sufficient increase to qualify for PD, taking as a reference the smallest sum diameters while on study.

NON-TARGET LESIONS	
Lesions Response:	Definition:
Complete Response (CR)	Disappearance of all non-target lesions and normalization of tumor marker level. All lymph nodes must be non-pathological in size (< 10-mm short axis)
Non-CR/Non-PD	Persistence of one or more non-target lesion(s) and/or maintenance of tumor marker level above the normal limits.
Progressive Disease (PD)	Unequivocal progression of existing non-target lesions (see definition below).

Progression in Non-target Disease:

There must be an overall level of substantial worsening in non-target disease such that, even in the presence of stable disease (SD) or partial response (PR) in target disease, the overall tumor burden has increased sufficiently to merit discontinuation of therapy.

Because worsening in non-target disease cannot be easily quantified, a useful test that can be applied when assessing patients for unequivocal progression is to consider if the increase in overall disease burden based on the change in non-measurable disease is comparable in magnitude to the increase that would be required to declare progressive disease (PD) for measurable disease (i.e., an increase in tumor burden representing an additional 73% increase in “volume” [which is equivalent to a 20% increase in the diameter of a measurable lesion]).

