10.1.3.2. Objective Response Assessment

Assessments will be based on the definitions provided in [Table 13](#) and [Table 14](#).

Table 13: Time Point Response for Patients with Target (+/- Non-Target) Disease

Target Lesions	Non-Target Lesions	New Lesions	Objective Response
CR	CR	No	CR
CR	Non-CR/Non-PD or Not all evaluated	No	PR
PR	Non-PD or Not all evaluated	No	PR
SD	Non-PD or Not all evaluated	No	SD
Not all evaluated	Non-PD	No	Not evaluable
PD	Any	Yes or No	PD
Any	PD	Yes or No	PD
Any	Any	Yes	PD

Abbreviations: CR = complete response; PD = progressive disease; PR = partial response; SD = stable disease

Table 14: Time Point Response for Patients with Only Non-Target Disease

Non-Target Lesions	New Lesions	Objective Response
CR	No	CR
Non-CR/Non-PD	No	SD
Not all evaluated	No	Not evaluable
Unequivocal PD	Yes or No	PD
Any	Yes	PD

Abbreviations: CR = complete response; PD = progressive disease; SD = stable disease

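### Protocol 10.1.2 gives two conflicting rules for the primary tumour; wherever the always-non-target rule is followed, a patient measurable only in the primary can never be scored PR

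*Protocol*

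**What the plan says.** **Lesion selection.** Protocol 10.1.2, under Target Lesions, wants "All measurable lesions up to a maximum of 2 lesions/organ and 5 lesions in total" taken as targets and makes no exception for the primary. Under Non-target Lesions the same section says: "The primary lesion should always be classified as a non-target lesion irrespective of its size and whether or not it can be accurately measured".

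**Response scoring.** Protocol 10.1.3.1 defines PR as "At least a 30% decrease in the sum of diameters of the target lesions". Non-target disease progresses by "Unequivocal progression of existing non-target lesions". Patients without a target lesion are scored from Table 14, "Time Point Response for Patients with Only Non-Target Disease".

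**Eligibility and denominator.** Phase 2 enrols "locally advanced, metastatic, unresectable iCCA harboring FGFR2 gene fusions or other FGFR2 rearrangements" (inclusion 3b). Inclusion 4 reads "Patient has measurable disease as defined by Response Evaluation Criteria in Solid Tumors (RECIST) guidelines" and does not ask for measurable disease outside the primary. The Phase 2 Efficacy Population (Phase 2 SAP 5.3) contains every iCCA patient with an FGFR2 fusion or rearrangement who took at least one dose.

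**Readers.** Protocol 10.1 opens with "The determination of antitumor efficacy will be based on objective tumor assessments made by the investigator", then says that primary endpoints rest on independent review. The Phase 2 SAP takes the primary ORR from independent review under RECIST 1.1 (3.2.1, 6.4.1) and uses investigator reads for sensitivity analyses of ORR and PFS (6.4.2.1). The Phase 1 Expansion SAP (4.2) takes ORR from the investigator for tumour types other than CCA and CNS.

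**The concern.** The two sentences in 10.1.2 cannot both be followed for a measurable primary. Even if the second is read as a deliberate exception to the first, it leaves some eligible patients with no target lesion, and so with no route to the most likely kind of response. A 30% shrinkage in such a patient is scored SD.

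There are two things at stake. First, any ORR read under the second sentence is understated for these patients. Second, if site and independent readers followed different sentences, the Phase 2 investigator-read analysis differs from the primary analysis in lesion rule as well as in reader. It then no longer isolates the effect of the reader, which is its purpose.

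**Working it through.** **1. The plan's own threshold.** Phase 2 SAP 6.4.1 rejects a 10% ORR if the two-sided 95% Clopper-Pearson lower bound exceeds 10%, which it gives as at least 17 of 100. The lower bound is 9.43% at 16/100 and 10.23% at 17/100, so 17 is right. The exact one-sided type I error at 10% is 0.0206.

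**2. Tracing one patient.** Take a patient whose only measurable lesion is the primary.

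| Step | Primary may be a target | Primary always non-target |
|---|---|---|
| Inclusion 4 | Met | Met |
| Target lesions | The primary | None |
| Response table | Table 13 | Table 14 |
| Possible outcomes | CR, PR, SD, not evaluable, PD | CR, SD, not evaluable, PD |
| In ORR denominator | Yes | Yes |

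Every PR row in Table 13 needs target lesions in CR or PR, and Table 14 has no PR row. CR stays possible, but needs all non-target lesions to disappear and tumour markers to normalise. One other measurable lesion restores PR. For patients with other targets, leaving the primary out of the sum could move ORR either way.

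**3. Can such patients enrol?** Yes, if the disease descriptors in inclusion 3b are alternatives, or if the patient's metastases are not measurable. Protocol 5.1 treats locally advanced and metastatic disease as separate stages, and the Phase 1 Expansion SAP (6.3.2) tabulates patients with locally advanced disease only. No document gives their number.

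**4. SAP coverage.** Phase 2 SAP Table 4 has no row for a patient without a target lesion. Protocol Table 14 and dose-escalation SAP Table 8 do cover that case.

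**5. Size, for illustration.** Let p be the ORR when the primary may be a target, and f the share of treated patients measurable only in the primary. Assume no CR among them and response unrelated to f. Then scored ORR = p(1 − f), and the loss is p × f. Protocol 5.6 reports 3 confirmed PRs in 14 patients, so p = 3/14 = 21.4% (exact 95% CI 4.7 to 50.8%); p = 30% is assumed.

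| f (assumed) | Loss at p = 21.4% | Loss at p = 30% |
|---|---|---|
| 5% | 1.1 points | 1.5 points |
| 10% | 2.1 points | 3.0 points |
| 20% | 4.3 points | 6.0 points |

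**6. Effect on the Phase 2 test, only if the independent readers used the non-target sentence.** Power = P(X ≥ 17) for X ~ Binomial(100, p(1 − f)).

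| f | p = 21.4% | p = 25% | p = 30% | Rejection probability at p = 10% |
|---|---|---|---|---|
| 0 | 0.888 | 0.979 | 0.999 | 0.0206 |
| 5% | 0.831 | 0.960 | 0.997 | 0.0130 |
| 10% | 0.756 | 0.929 | 0.993 | 0.0078 |
| 20% | 0.556 | 0.808 | 0.965 | 0.0024 |

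Phase 1 reads were local (protocol 12.2.2.1), so 3/14 may already reflect the sentence. In that case, with the same f, the underlying rate is (3/14)/(1 − f) = 22.6, 23.8 and 26.8%. Power is then 0.888 with the sentence, against 0.930, 0.961 and 0.992 without it.

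**7. PFS.** Without target lesions, the 20% rule on the target sum does not apply. But protocol 10.1.3.1 suggests judging non-target progression against a 73% volume increase, equivalent to 20% in diameter (1.2³ = 1.728). The effect on PFS should be small.

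**The case against.** **A reader might infer that the Phase 2 primary ORR is understated and the trial underpowered.** The documents do not support this. That ORR comes from independent review under RECIST 1.1. The readers' target-selection rule is not in the supplied text, and the Imaging Manual cited in protocol 10.1.1 is not among the documents. The 0.556 power figure needs a low p, f = 20%, independent readers using the sentence and no CRs, all at once. The Phase 2 sample-size text is redacted, so 21.4% is not known to be the planning rate. At p = 30%, power stays at 0.965 or above for f up to 20%.

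**A reader might infer that the site reads at least are certainly affected.** This is not established either. Section 10.1 names the investigator, but 10.1.2 is not confined to on-site reads, and sites also face the instruction to take all measurable lesions as targets. The effect on site reads also depends on which sentence was followed.

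**The bias is conservative.** This stands: the rejection probability at p = 10% falls from 0.0206.

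**The SAP gap is minor, because protocol Table 14 already gives the outcomes.** This stands as to the remedy: a cross-reference is enough.

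**Simply deleting the sentence would not help.** This also stands. Baselines already read would keep the old rule, leaving two rules in one analysis. The Phase 2 SAP is dated 15 October 2020 and its revision history refers to efficacy data on all enrolled patients, so few new baselines may remain. On-site reads also guide whether treatment continues (protocol 9.17.1), so the change proposed here must be limited to response scoring.

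None of this removes the contradiction or restores PR for these patients under the second sentence.

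**Conclusion.** The point holds in a conditional form and is worth fixing. Protocol 10.1.2 contradicts itself on whether a measurable primary can be a target lesion. Wherever the always-non-target sentence is applied, an eligible patient measurable only in the primary cannot be scored PR yet counts in the ORR denominator.

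Three results are exposed, each according to the sentence its reader followed: the Phase 2 independent primary ORR, the Phase 2 investigator-read sensitivity ORR, and the investigator-read Phase 1 Expansion ORR. For these patients the error lowers ORR and does not inflate type I error. Its size, p × f, cannot be fixed because f is not in the documents; 1.1 to 4.3 points at p = 21.4% is an illustration resting on an assumed f of 5 to 20%. No figure can be given for the Phase 1 Expansion groups, whose sizes are not in the text.

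**What to change.** 1. **Reconcile the two sentences in protocol 10.1.2** into one target-selection rule for response scoring, under which an eligible patient measurable only in the primary can be scored PR. State that it covers both independent and investigator reads. How this bears on on-site treatment decisions is for the sponsor to reconcile.
2. **Confirm the rule actually used**, from the Imaging Manual and the core imaging laboratory for the independent read and from the sites for theirs, and record it for each read.
3. **In Phase 2 SAP 6.4.1, cross-reference protocol Table 14** for any patient in whom a reader selects no target lesion.
4. **Keep the pre-specified primary read.** If any reads used the non-target sentence, report how many patients were measurable only in the primary. If the independent read did, add one sensitivity ORR with target lesions re-selected from baseline images, blind to later response.

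The cost is a short protocol clarification that must go through the amendment process (protocol 14.1), a query to the imaging laboratory and possibly one extra sensitivity table with a limited baseline re-read. The primary analysis does not change.
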